Address: Breast Imaging SWLBSS Rose Centre, St George's University Hospitals NHS
Foundation Trust, [name]

Email: [contact]

1. Introduction

2 Trial Objectives, Design and Statistics

- 2.1. *Trial Objectives*
- 2.2 *Trial Design*
- 2.3 *Trial Flowchart*
- 2.4 *Trial Statistics*
- 2.5 *Economic analysis*

3. Sample Size, Selection and Withdrawal of Subjects

- 3.1 *Inclusion*
- 3.2 *Exclusion*
- 3.3 *Criteria for Premature Withdrawal*

4. Study procedures

- 4.1 *Informed Consent Procedures*
- 4.2 *Randomisation Procedures*
- 4.3 *End of Study Definition*

5. NHS Breast Screening Services - trial procedures

- 5.1 *Mammography Examinations*
- 5.2 *Image Storage*
- 5.3 *Mammography Film Reading*
- 5.4 *Results of Mammography Film Reading*
- 5.5 *Data Recording/Reporting*
- 5.6 *Image Transfer to Other Sites*
- 5.7 *Trial Site Service Quality*

6. Assessment of Safety

- 6.1 *Risk from Ionising Radiation*
- 6.2 *Ethics Reporting*

7. Trial Steering Committee

8. Ethics & Regulatory Approvals

9. Data Handling

- 9.1 *Confidentiality*
- 9.2 *Trial Participant Data Record*
- 9.3 *Archiving*
- 9.4 *Compliance*
- 9.5 *Clinical Governance Issues*
- 9.6 *Non-Compliance*

10. Finance & Publication Policy

Study Synopsis

Title	Prospective Randomised Trial of Digital Breast Tomosynthesis (DBT) Plus Synthetic 2D Mammography (S 2D) compared to Standard 2D Digital Mammography in Breast Cancer Screening.
Protocol Short Title/Acronym	PROSPECTS
Protocol Version number and Date	Version
Is the study a Pilot?	No
Study Duration	Seven years
Methodology	Randomised controlled trial
Sponsor Name	King's College Hospital NHS Foundation Trust
Chief Investigator	[name] [name]
REC Number	17/LO/0054
IRAS Number	199080
Medical Condition or Disease under Investigation	Breast Cancer
Purpose of Clinical Trial	To measure the cost-effectiveness of DBT and S2D compared to standard 2DDM in breast cancer screening
Primary Objective	To compare the cost-effectiveness of breast cancer screening using DBT + S2D with screening using 2DDM by measuring cancer detection rates, interval cancer rates, size and lymph node status of Grade 2 and 3 invasive cancers in intervention (DBT + S2D) and 2DDM (standard care) groups.
Secondary Objective (s)	
 1.To demonstrate non-inferiority of S2D + DBT compared to 2DDM + DBT in breast cancer screening. 2.To measure the impact of DBT + S2D screening on screening recall rates, benign biopsy rates at diagnostic assessment and at surgery. 3.To measure the effect of DBT + S2D screening compared to 2DDM in patient groups according to breast density, type of screen, age. 4.To develop methods for measuring reader performance with DBT + S2D screening. 5.To carry out retrospective reader studies to measure the effect of other screening strategies – 2DDM vs DBT alone, 2DDM vs 2DDM + limited tomosynthesis views. 6.To compare patient preferences for breast cancer screening with 2DDM + DBT or S2D vs 2DDM. 7. To develop & evaluate Artificial Intelligence Algorithms for the Analysis of DBT images
Number of Subjects/Patients	100,000
Trial Design	Prospective randomised controlled trial
Endpoints	Primary end-points Invasive cancer detection rates

	
Size and lymph node status of grade 2 and 3 invasive cancers Interval cancer rates Cost of screening with DBT + S2D vs. screening with 2DDM alone Mammography reading time for 2DDM, DBT + S2D
 
Secondary end-points
 
 1.Cancer detection rates using DBT + 2DDM compared to DBT + S2D 2.Recall rates 
Benign biopsy rates at assessment Benign surgical biopsy rates
 
 3.Measurement of cancer detection rates, recall rates in subgroups of women in intervention and control groups defined by breast density, type of screen, age group. 4.Development of a method for measurement of reader performance. 5.Results of retrospective reader studies to compare different screening strategies and costs including DBT alone, S2D + limited tomo views. 6.Measurement of trial participant experience of DBT + 2DDM vs S2D 7. Demonstration of the effectiveness of Artificial Intelligence in the analysis of DBT images
Main Inclusion Criteria	Women aged 49-71 years attending for routine breast screening.
Statistical Methodology and Analysis	See sections 2.4 and 3.

The trial involves use of a commercially available mammography machine capable of 2DDM and DBT (Hologic Dimensions Mammography machine). The equipment is CE marked and is in use in departments for diagnostic work up mammography for clients recalled following screening. Further information about the equipment can be obtained from the manufacturer’s website.

Glossary of Terms and Abbreviations

AE	Adverse Event
AR	Adverse Reaction
ASR	Annual Safety Report
CA	Competent Authority
CI	Chief Investigator
CRF	Case Report Form
CRO	Contract Research Organisation
DMC	Data Monitoring Committee
EC	European Commission
GAfREC	Governance Arrangements for NHS Research Ethics Committees
ICF	Informed Consent Form
ISRCTN	International Standard Randomised Controlled Trial Number
MA	Marketing Authorisation
MHRA	Medicines and Health Regulatory Authority
MS	Member State
Main REC	Main Research Ethics Committee
NHS R&D	National Health Service Research & Development
PI	Principle Investigator
QA	Quality Assurance
QC	Quality Control
Participant	An individual who takes part in a clinical trial
RCT	Randomised Controlled Trial
REC	Research Ethics Committee
SAE	Serious Adverse Event
SDV	Source Document Verification
SOP	Standard Operating Procedure
SSA	Site Specific Assessment
TMG	Trial Management Group
TSC	Trial Steering Committee
SUSAR	Suspected Unexpected Serious Adverse Reaction
UADE	Unexpected Adverse device Reaction
CAPA	Corrective And Preventive Action

SAR	Serious Adverse Reaction
SADE	Serious Adverse Device Event
GCP	Good Clinical Practice
MHRA	Medicines and Healthcare Products Regulatory Agency

1. Introduction

The accuracy of two view digital x-ray mammography (2DDM), the standard test for breast cancer screening, is limited because of the effect of superimposition of normal breast structures onto a two dimensional image. The mammography signs of breast cancer may be obscured, particularly in women with dense fibro glandular breast tissue (Al Mousa, DS. et al 2014), resulting in delay in diagnosis of cancer. National interval cancer data shows that up to 4000 women per annum (2.88 per 1000 screened) are diagnosed with breast cancer in the interval between screens (Offman, J. & Duffy, S. 2012). Conversely, superimposition of normal tissues may produce features on mammography which are suspicious for cancer and lead to unnecessary recall for further diagnostic tests. National screening data for 2012/2013 show that of 2.3 million women screened, 79000 (3.4%) without breast cancer were recalled to specialist diagnostic assessment clinics (Centre for Cancer Prevention, 2014).

DBT is an x-ray mammography technique which involves acquiring multiple low dose projections over a limited angular range (less than 50 degrees). These projection images are reconstructed into a set of images consisting of parallel planes, typically 1mm apart throughout the breast. Three dimensional information is provided for the reader, overcoming many of the interpretation problems associated with 2DDM. Several studies have demonstrated improvement in the accuracy of DBT in the diagnostic setting (Brandt, K. et al 2013 & Morel, J. et al 2014) Published data from studies of DBT combined with 2DDM in screening have demonstrated increased rates of invasive cancer detection, cancers detected at a smaller size and decreased false positive recall rates (Skaane, P. et al 2013, Ciatto, S. et al 2013 & Friedwald, S. et al 2014). However, there may be increased costs associated with the technology, image data storage and longer reading time (Bernardi, D. et al 2012).

As a result of recent technical developments, a two dimensional mammography image can be produced by processing the tomosynthesis image data. Synthetic 2D (S2D) trial data show that the accuracy of DBT + S2D may be the same as that achieved with DBT + 2DDM

The primary aim of this trial is to assess the impact of DBT and S2D or 2DDM in routine breast cancer screening compared to 2D mammography. Up to 100 000 women will be recruited using NHS screening sites with DBT ready mammography equipment. At each site, through a clinic randomisation process, the trial participants will undergo either standard 2DDM (the control group) or S2D and DBT (the study group). Synthetic 2D images will be produced for all women in the intervention group.

One concern about using DBT in conjunction with 2D imaging is the increase in radiation dose. We conservatively estimate the mean glandular radiation dose of 4.3 mGy in the control group and 5.3 mGy in the study group. A recent study of (Yaffe & Mainprize 2011) has shown that benefits of screening with mammography greatly exceed the detriment due to the radiation. Using similar calculations we estimate that the ratio of lives saved and lost due to radiation in the 2DDM screening arm will be in the range 150-300 to 1. The higher dose in the study group is expected to lead to greater benefit and greater detriment. In order for the extra benefit to exceed the extra detriment of using DBT in the study group there will need to be a very small (0.05 to 0.1%) increase in lives saved. In practice we expect a larger benefit than this.

- Health need: the effectiveness of 2DDM in detection of invasive breast cancer has improved over the last twenty years as demonstrated by a decrease in interval cancer rates (cancers occurring between routine three yearly screens) (Offman, J. & Duffy, S. 2012). This improvement is a result of the introduction of two view mammography, digital mammography and

improvements in film reading performance. However, the most recent published interval cancer rates of 2.85 per 1000 women screened demonstrates the limited sensitivity of 2DDM in cancer detection. Published data from studies of DBT and 2DDM in screening in Europe and North America demonstrate an increased invasive cancer detection rate of 40-48% compared to 2DDM alone (Skaane, P. et al 2013 & 2014, Ciatto, S. et al 2013, Friedwald, SM. Et al 2014 & Zackrisson, S. et al 2014). Data from this study will demonstrate whether such an improvement in sensitivity is achievable in the NHSBSP, whether cancers can be detected at a smaller size, and prognostic features of screen detected and interval cancers will be used to model whether there would be a greater reduction in breast cancer mortality from screening with 2DDM plus DBT compared to 2D alone. Data will also demonstrate the effect on false positive recalls in the NHSBSP. Published results show that this may be decreased by 15-20% with the use of DBT.

- Economic analysis: The study will demonstrate whether replacing standard 2DDM with DBT (and S2D) represents an efficient use of NHS resources, either because DBT reduces overall cost or because the additional health benefits of greater sensitivity and specificity justify the additional cost.
- Sustained interest: DBT may have a major impact on the effectiveness and the cost of screening. Data from this study will help decide the optimum strategy for using DBT in routine screening in the NHS.
- Development of research area: results from this study will help identify which groups of women will benefit from screening with DBT.
- Scientific knowledge: this study will advance our understanding of the effect of DBT on the characteristics of screen detected cancers, whether more biologically significant cancers are found when smaller and at an earlier stage, and whether more low grade cancers are diagnosed, increasing the problem of over diagnosis.

Literature Review.

1. The technical aspects of digital breast tomosynthesis have been reviewed (Sechopoulos, I. 2013, Gilbert, FJ. 2010).

2. Clinical studies measuring the accuracy of DBT compared to 2DDM in breast cancer detection have been reviewed (Houssami, N. & Skaane, P. 2013 & Alakhras, M. et al 2013). These studies measured the performance of readers in the interpretation of test sets or clinical series of cases, either symptomatic or screening recalls, usually with a high proportion of cancers. The data demonstrates that two view DBT has at least equal or better accuracy than standard 2DDM, and that the addition of DBT to 2DDM improves reader accuracy (Michell, MJ. et al 2012, Rafferty, EA. et al 2013, Gilbert, FJ et al 2014).

3. Screening Studies using DBT.

A systematic search of the literature has been performed (medline and embase databases, 2010 – 2015, search terms 'tomosynthesis' 'screening').

A review of the literature identifies 8 retrospective studies (Lourenco, AP. Et al 2015, Durand, MA. Et al 2015, McCarthy, AM. et al 2014, Greenberg, JS. et al 2014, Friedwald, SM. et al 2014, Destounis, S. et al 2014, Haas, BM. et al 2013 & Rose, SL. et al 2013) and 3 prospective studies (Ciatto, S. et al 2013, Skaane, P. et al 2013, 2014, Zackrisson, S, et al 2014) of DBT in addition to 2DDM in screening. All the studies report an increase in cancer detection when using DBT. In the three prospective studies and the largest retrospective study the increase in cancer detection rate ranges from 27% - 51%. This is due to an increase in invasive cancer detection with no significant change in DCIS rate. Most of the studies show a decrease in the false positive recall rate of 15-20%. In one study the recall rate increased from 2.6 to 3.8% but the PPV remained unchanged indicating that the increase in recall rate from a very low base was matched by an increase in cancer detection (Zackrisson, S. et al 2014). There is limited data on

the pathological characteristics of the additional cancers detected by DBT. In the Oslo study, 60% of the additional cancers were Grade 1 and 40% were Grade 2 or 3 (Skaane, P. et al 2013).

There remains debate over the use of DBT in large scale population breast screening programmes because of uncertainty about costs of implementation including reading time, data storage and transfer and the effect of DBT on the efficacy of screening and over diagnosis (Gilbert, F. et al 2016). The biological significance of DBT screening detected cancers can be demonstrated by examining their prognostic features and interval cancer rates (Evans, A. 2015).

- We propose a prospective randomised trial to measure the effect on cancer detection and recall rate of screening with DBT + S2D compared to 2DDM alone. Data on the numbers and pathological characteristics of the cancers diagnosed by screening and those found as interval cancers will be used to calculate the effect of DBT on the numbers of breast cancer deaths prevented and the number of Quality Adjusted Life Years (QALYs) gained.
- The cost implications of using DBT in routine screening relating to technology, IT and data storage, image reading time and assessment practice will be calculated. In combination with the estimated gain in QALYs, the cost-effectiveness in terms of the additional cost per QALY will be calculated.
- The data will be analysed to measure any differences in the effect of screening with DBT + S2D in different patient subgroups identified by breast density, type of screen and age.
- Retrospective reader studies will be carried out to assess other mammography screening strategies including use of synthetic 2D mammography.
- The target population for this trial is women aged 49-71 years attending for routine mammography screening.
- The new technology being evaluated is digital breast tomosynthesis (DBT).
- Patient experience of DBT + S2D vs 2DDM will be assessed.

The comparator technology is two dimensional digital mammography (2DDM) which is the current standard test for routine breast cancer screening.

2 Trial Objectives, Design and Statistics

2.1. Trial Objectives

Primary objectives.

To compare the cost – effectiveness of breast cancer screening using DBT + S2D with screening using 2DDM by measuring cancer detection rates, interval cancer rates, size and lymph node status of Grade 2 and 3 invasive cancers in intervention (DBT + S2D) and 2DDM (standard care) groups.

Secondary objectives.

1. To demonstrate non-inferiority of DBT + S2D compared to DBT + 2DDM.
2. To measure the impact of DBT +2DDM or S2D screening on screening recall rates, benign biopsy rates at diagnostic assessment and at surgery.
3. To measure the effect of DBT + 2DDM or S2D screening compared to 2DDM in patient groups according to breast density, type of screen, age.
4. To develop methods for measuring reader performance with DBT + 2DDM or S2D screening.

5. To carry out retrospective reader studies to measure the effect of other screening strategies – 2DDM vs DBT alone, 2DDM vs DBT + synthetic 2D, 2DDM vs 2DDM + limited tomosynthesis views.
6. To compare patient preferences for breast cancer screening with DBT +2DDM or S2D vs 2DDM.
7. To develop & evaluate Artificial Intelligence Algorithms for the Analysis of DBT images.

Primary end-point.

Invasive cancer detection rates

Interval cancer rates

Size and lymph node status of grade 2 and 3 invasive cancers

Cost-effectiveness of screening with DBT + 2DDM or S2D vs screening with 2DDM.

Secondary end-point.

[figure not shown]
1. Measurement of invasive cancer detection rates using DBT + 2DDM or S2D vs 2DDM
2. Recall rates
Benign biopsy rates at assessment
Benign surgical biopsy rates
3. Measurement of cancer detection rates, recall rates in subgroups of women in intervention and control groups defined by breast density, type of screen, age group.
4. Development of a method for measurement of reader performance.
5. Results of retrospective reader studies to compare different screening strategies including 2DDM + synthetic 2D, DBT alone, 2DDM + limited tomo views.
6. Measurement of trial participant experience of DBT + 2DDM vs 2DDM.
7. Demonstration of the effectiveness of Artificial Intelligence in the analysis of DBT images.

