2.2 Trial Design

Randomised controlled trial.

Women aged 49-71 years attending for routine mammography screening will be randomised by batch/clinic to either standard care group (2DDM) or intervention group (DBT + S2D). The images will be double read by NHS BSP film readers fulfilling NHS BSP QA criteria for film reading and who have undergone training in DBT image interpretation. The results of film reading will be recorded on the National Breast Screening Computer System (NBSS) and then complete data (with surgical and pathology data where appropriate) will be downloaded for statistical analysis. The initial trial recruitment period will be the length of time required to reach the recruitment target of up to 70,000 women by 8 NHSBSP screening centres.

Interval cancer data will be collected as per routine by the screening centres in collaboration with Cancer Registries and QA Reference Centres.

2.3. Trial Strategy and Recruitment.

1. Recruitment.

Up to 09.2023, the trial has recruited over 36,000 women from 6 screening centres, randomized 1:1 between the control group (standard 2DDM) and the intervention group (DBT and 2DDM/synthetic 2D). Two further sites are starting recruitment this autumn – Leicester, St George’s London. We do not anticipate increasing the number of trial sites above 8.

The overall recruitment rate is just over 50% of those who attend screening and are invited to participate. The participation rate varies between the sites (26%-81%) and reflects differences in the local population demographics. Participation is higher at static sites compared to mobile screening sites. We have examined ways of increasing participation rates including

- different consent processes – face to face, phone and online;
- revision of the patient information materials;
- investment in staff time to facilitate consenting.

We estimate that trial recruitment will continue at between 1500 and 2000 per month with 8 recruiting sites.

2. Strategy.

We propose a strategy to ensure that there are sufficient numbers of women recruited to each arm of the trial in order to address the principal objectives of the trial and to ensure that the trial is completed and results available within the funding available, and within a reasonable timeframe in relation to ongoing discussions about application of new technology to the national screening programme.

3. Randomization ratio.

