We have therefore considered changing the randomization ratio in favour of the intervention arm and decreasing the overall recruitment target. We conclude that the randomization ratio could be changed to 1:3 (control:intervention) and the overall target recruitment changed to 70,000. This would provide sufficient data to address the impact of DBT screening on interval cancer rates and cancer detection. We plan to augment the trial analysis with a further secondary analysis, comparing endpoints between our intervention group and figures from the national programme, using standardised incidence ratios.

Table 1. Estimate of numbers recruited in control and intervention groups to 03.2025, with a 1:3 randomization ratio from 01.2024

			Control	Intervention	Total
To 09.2023			18,000	18,000	36,000
To 12.23			20,000	20,000	40,000
01.24 - 03.25 @1:3	control	intervention			
1500/month	5625	16,875	25,625	36,875	62,500
2000/month	7500	22,500	27,500	42,500	70,000

4. Invasive cancer detection rates.

For a comparison of invasive detection rates (the first primary endpoint), if we posit 9 per thousand in the DBT arm and 7 in the control, we will have approximately 80% power with the totals assuming recruitment of 1,500 per month and in excess of 80% power with 2,000 per month (5% significance level, 2-sided testing). Thus even without the use of the routine screening data, we will have sufficient power for the first primary endpoints.

5. Interval cancer rates.

Assuming the national rate of interval cancers in the control group, 3.5 per 1000 over 3 years, and if we assume conservatively that the reduction is 25% less than the increase in invasive detection rates, we would anticipate a rate of 2 per 1000 in the intervention arm.

Our totals for recruitment of 1,500 per month would yield in excess of 90% power to detect this as significant (5% significance level, two-sided testing). Thus we will be powered for this too.

6. As noted above, we also propose to carry out age-standardised comparison of these endpoints with those observed nationally, since the latter give highly precise estimates of outcomes for usual care. However, we re-emphasise that the primary analyses will be the protocol-specified randomised trial comparisons.

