We assume that the yield of cancers in the control group will be 8 per thousand as previously observed in the NHSBSP (more recent figures suggest closer to 9 per thousand, but we work with 8 per thousand to be conservative). We might reasonably expect this to be 6 per thousand in the intervention arm due to increased prior detection rates with DBT. With 36,875 women in the intervention arm and 25,625 in the control arm, we will have more than 80% power to detect such a difference as significant (5% significance, 2-sided testing). Thus, even with the conservative assumption of 1,500 recruitment per month, the study will be adequately powered for this comparison.

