- If a woman accepts the invitation to participate, she will undergo either standard 2DDM/S2D and DBT according to the clinic randomisation procedure. After the first 25,000 women have undergone 2DDM and DBT, women entered into the interventional arm will undergo DBT and S2D.
- Women will no longer be provided a copy of the consent form at their appointment, if a women wishes to receive either an electronic or paper version of the consent form, she must contact the site using contact details on the PIS.

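### Secondary objective 1 promises non-inferiority of DBT + S2D to DBT + 2DDM, but the between-phase comparison of detection rates named for it cannot support that claim

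*Protocol*

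**What the plan says.** Section 2.1 lists as secondary objective 1 "To demonstrate non-inferiority of DBT + S2D compared to DBT + 2DDM"; the Synopsis has the same aim. The endpoint for it differs between the two places:

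- Synopsis, secondary endpoint 1: "Cancer detection rates using DBT + 2DDM compared to DBT + S2D".
- Section 2.1, secondary endpoint 1: "Measurement of invasive cancer detection rates using DBT + 2DDM or S2D vs 2DDM".

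Section 2.2 has women "randomised by batch/clinic to either standard care group (2DDM) or intervention group (DBT + S2D"), so 2DDM versus intervention is the only randomised contrast. Section 4.1 sets the order of the two DBT regimens: "After the first 25,000 women have undergone 2DDM and DBT, women entered into the interventional arm will undergo DBT and S2D".

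Section 2.3 and its Table 1 move allocation from 1:1 to 1:3 from January 2024 and report two further sites opening in autumn 2023. The same section gives the planning rates: "if we posit 9 per thousand in the DBT arm and 7 in the control".

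Three other statements bear on the point. The Introduction says that S2D images are made for every woman in the intervention group, and that retrospective reader studies will include synthetic 2D. Section 5.2 keeps raw images centrally for such studies. The radiation section says that available data already show the two DBT regimens to be equivalent in accuracy, and gives this as the reason to stop 2DDM in the intervention arm.

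**The concern.** The objective is worded as a confirmatory claim, but randomisation does not protect the comparison named for it. DBT + 2DDM women come first and DBT + S2D women later, so calendar time, site mix and reader experience can all differ between them. Section 2.3 reports participation from 26% to 81% by site, reflecting local demographics, so a change in site mix could move the underlying detection rate.

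Precision is the second problem. Detection is a rare event and the comparison splits one arm in two. If the interval is so wide that it could hide the loss of most or all of the DBT gain, a statement of non-inferiority from it would carry little information, yet would seem to confirm the equivalence that the radiation section already asserts.

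Third, the endpoint in section 2.1 puts both DBT regimens on the same side of the comparison. It says nothing about one against the other.

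**Working it through.** **Inputs.** Detection rates of 9 and 7 per 1,000 (section 2.3). Arm sizes at 1,500 a month: 36,875 intervention and 25,625 control; at 2,000 a month: 42,500 and 27,500 (Table 1). By December 2023: 20,000 per arm (Table 1). Switch at 25,000 intervention women (section 4.1). The margins are assumptions, because the Protocol states none.

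**1. The plan's own power.** For 9 vs 7 per 1,000 at two-sided 5% the Protocol states "approximately 80% power with the totals assuming recruitment of 1,500 per month and in excess of 80% power with 2,000 per month". Power = Φ((d − 1.96·SE0)/SE1), with SE0 pooled and SE1 unpooled, per 1,000.
- 25,625 vs 36,875: SE0 = 0.733, SE1 = 0.716; (2 − 1.436)/0.716 = 0.788, so 78.5%.
- 27,500 vs 42,500: SE0 = 0.699, SE1 = 0.680; power 82.3%.

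Both agree with the text. The Protocol gives no figure for S2D against 2DDM within the DBT arm.

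**2. Timing.** From 20,000 at the end of 2023, 5,000 more intervention women are needed. At 1:3 they arrive at 1,125 a month (three quarters of 1,500) or 1,500 a month (three quarters of 2,000). That takes 5,000/1,125 = 4.4 or 5,000/1,500 = 3.3 months. With a switch at 25,000, the S2D phase therefore lies wholly in the 1:3 period and after the two new sites were due to open.

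**3. Precision between phases.** SE = √[0.009 × 0.991 × (1/n1 + 1/n2)]; half-width = 1.96·SE; power = Φ(M/SE − 1.96) with true difference 0; margin for 80% power = (1.96 + 0.8416)·SE. Per 1,000:

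| | 25,000 vs 11,875 (1,500 a month) | 25,000 vs 17,500 (2,000 a month) |
|---|---|---|
| SE | 1.053 | 0.931 |
| 95% half-width | 2.06 | 1.82 |
| Power, margin 1 | 16% | 19% |
| Power, margin 2 | 48% | 57% |
| Margin for 80% power | 2.95 | 2.61 |

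**4. Sensitivity.** Moving the switch anywhere between 18,000 and 25,000 keeps the half-width at 1.8 to 2.1; a switch at 10,000 gives 2.1 to 2.2. An assumed design effect of 1.1 to 1.5 for clinic randomisation raises 2.06 to between 2.2 and 2.5.

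**5. Removing period drift through concurrent controls.** Controls up to the switch: 20,000 + 5,000/3 = 21,667. Controls after it: 25,625 − 21,667 = 3,958, or 27,500 − 21,667 = 5,833. At 7 per 1,000 the later controls yield about 28 or 41 cancers. The variance gains a term 0.007 × 0.993 × (1/21,667 + 1/3,958), an SE of 1.441 (or 1.230 with 5,833).
- 1,500 a month: half-width 1.96 × √(1.053² + 1.441²) = 3.5 per 1,000.
- 2,000 a month: half-width 1.96 × √(0.931² + 1.230²) = 3.0 per 1,000.
- As a ratio of two randomised rate ratios with true value 1: log SE 0.237 or 0.204, 95% CI 0.63-1.59 or 0.67-1.49.

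**6. Paired reading.** If all 25,000 women of the first phase were read both ways, half-width = 1.96 × √(ψ/25,000), where ψ is the proportion detected by one regimen only. For an assumed ψ of 0.5 to 3 per 1,000 this is 0.28 to 0.68 per 1,000, and power at a margin of 1 per 1,000 is above 99% down to 82%.

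**The case against.** The strongest reply is that the trial has a much better route to this objective. Women in the DBT + 2DDM phase have both image sets, raw images are kept for reader studies, and studies with synthetic 2D are planned. A within-woman comparison is free of period and site effects and, by step 6, far more precise. This stands. A reader might infer that the trial as a whole cannot show non-inferiority; the documents do not support that.

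The reply does not rescue the text as written. The Synopsis names detection rates for this comparison, and none of the reader contrasts in secondary objective 5 sets DBT + S2D against DBT + 2DDM. Retrospective reads also cannot fully verify lesions seen only on S2D.

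Margin and method commonly belong in the SAP, which is not shown. Their absence is therefore not part of this point. The imprecision does not depend on it: no margin that keeps any part of the 2 per 1,000 gain has adequate power here, and an SAP cannot supply randomisation between phases.

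Two further readings go too far. One is that S2D would replace 2DDM without evidence: the radiation section relies on separate attached data that cannot be judged from here. The other is that drift of a given size will bias the result: the Protocol gives no estimate of drift, so the risk is real but its size unknown.

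Finally, this is one of seven secondary objectives, and the randomised primary comparisons are unaffected.

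**Conclusion.** The point holds for the between-phase comparison of detection rates, and for that comparison only. It is not randomised, and its half-width about equals the whole planned DBT gain; the full interval, 3.6 to 4.1 per 1,000, is about twice that gain. Even a margin equal to the entire gain would leave power near one half. The endpoint in section 2.1 cannot test the objective at all.

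The figures assume 9 per 1,000 in both regimens, no true difference, one-sided 2.5% and independent women. Clustering by clinic would widen the interval. The 9 per 1,000 is the planning rate for invasive cancers; the Synopsis endpoint says cancers without that limit, and a higher rate would also widen the absolute interval.

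Overlap with the allocation change and the new sites depends on the switch at 25,000. The Protocol is not consistent on this: section 4.1 says 25,000 women, the radiation section refers to the first 50,000 (which fits 25,000 per arm under 1:1) and then proposes to stop 2DDM, section 2.2 describes the intervention simply as DBT + S2D, and section 2.3 describes recruitment to September 2023 as either regimen. An earlier switch would change the timing argument and the figures of steps 5 and 6, but would barely change the half-widths of step 3.

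**What to change.** 1. Reword secondary objective 1, in the Synopsis and in section 2.1, as estimating the difference in detection between DBT + S2D and DBT + 2DDM with a 95% CI. Describe it as a non-randomised between-phase comparison and drop the promise to demonstrate non-inferiority from it.
2. Make secondary endpoint 1 in section 2.1 match the Synopsis, and say in both places whether it counts invasive cancers or all cancers.
3. As a sensitivity analysis for period drift, report the contrast adjusted through each phase's concurrent controls, stratified by site. State in advance that its half-width is about 3.0 to 3.5 per 1,000 with a switch at 25,000, so that it is not read as the more precise result.
4. If a non-inferiority claim is kept, tie it to a paired reading of the DBT + 2DDM phase within the planned reader studies, and state the limit on verifying lesions seen only on S2D.
5. Reconcile sections 2.2, 2.3 and 4.1 and the radiation section on when 2DDM stopped in the intervention arm.

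Items 1, 2, 3 and 5 need only protocol wording and data already being collected. Item 4 costs reader time, and reading fewer than 25,000 women would give less precision than step 6 shows. What is given up is a confirmatory secondary claim that the between-phase data could not have supported.
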